#### 7 Data Sets to be Analyzed

Subjects in this study must be in accordance with the criteria specified below. Subjects who do not meet all inclusion criteria, disease diagnostic criteria, or who meet any exclusion criteria may not be randomized into the study without prior approval from the Project Directors and Medical Monitor. Membership in the analysis sets will be determined in a Pre-Analysis review meeting (see Section 8.2) before unblinding.

The following analysis sets will be used for the statistical analysis and presentation of data:

- The Enrolled set (ES) will include all subjects who signed IC and meet all inclusion and exclusion criteria. All data collected from ES will be presented in listings and if relevant in tables and/or graphs. Screening failures will have selected data be presented in a separate listing if needed.
- The Intent-to-Treat set (ITT) will consist of all subjects who are randomized. The primary efficacy analyses will be based on the ITT.
- The Modified Intent-to-Treat set (mITT) will consist of all subjects who randomized, take at least 1 dose of the study drug, and have at least 1 post-baseline assessment. The mITT will be used to support the primary efficacy analyses.
- The Safety analysis set (SAF) will be the primary safety analysis set and will consist of all
  randomized subjects who receive at least 1 dose of the study drug. The safety analyses will
  be based on the SAF.
- The Per-protocol set (PPS) will consist of all mITT subjects who complete at least 145 days treatment exposure (Last dose date First dose date + 1 >= 145 days) without any major protocol deviations that potentially could impact the primary efficacy endpoint. The PPS will be used to support the primary and secondary endpoints as supportive analyses.
- The PK set will analyze all available data from safety subjects receiving buntanetap and with at least one sampling profile allowing derivation of at least one PK parameter. Intense PK

subgroup is only in the US. 16-people per group will go through 10hr sampling timepoints at 0, 1hr, 1.5hr, 2hr, 3hr, 4hr,5hr, 6hr, 7hr, 8hr, 9hr, and 10hr (±10 mins for all collection timepoints).

Protocol deviations leading to exclusions from PPS include but are not limited to the following:

- Non-fulfilment of all inclusion criteria
- Fulfilment of at least one exclusion criterion
- Use of certain concomitant medications (for details see section 8.3.11)

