#### 8.3.11.3 Coding and imputation of incomplete dates

All concomitant medications/therapies will be classified according to ATC level 3 group text and WHO Drug Dictionary PT. The medications will be classified into categories Prior and Concomitant drug administration based on start date and end date in relation to IMP exposure.

- Prior medications are those for which end dates of the medication/therapy are strictly before date of first administration of study drug.
- Concomitant medications are those for which the period between their start dates and end dates coincide with exposure to study drug and can be further classified into:
  - Concomitant medications starting prior to first exposure to study drug having start dates strictly before first exposure to study drug and end dates on same date or after date of first administration to study drug or are ongoing.
  - Concomitant medications starting on the date of first administration of study drug or after but before or on the date of last administration of study drug

For medication and therapies with partial dates:

- If start date is completely missing, it will be assumed that the medication started before date of first administration of study drug.
- If end date is completely missing and ongoing is not ticked, it will be assumed that the medication ended before date of first administration of study drug.
- o If the only the year is available, month 6 will be imputed for the purpose of classification.
- For medications/therapies where only year and month (including imputed dates) are available this information will be used in analogy with how complete dates are used for classification, e.g.:

Start date	End date	Ongoing	IMP start date	IMP end date	Classification
2020-07	2020-07		2020-08-14	2020-09-13	Prior
2020-07		No	2020-08-14	2020-09-13	Prior
2020-07		Yes	2020-08-14	2020-09-13	CM before
2020-07	2020-08		2020-08-14	2020-09-13	CM before
2020-08	2020-08		2020-08-14	2020-09-13	CM before
2020-08		No or Yes	2020-08-14	2020-09-13	CM before
2020-08	2020-09		2020-08-14	2020-09-13	CM before
2020-09	2020-09		2020-08-14	2020-09-13	CM after
2020-09		No or Yes	2020-08-14	2020-09-13	CM after

CM: Concomitant Medication

A relative day will not be calculated for medications with incomplete dates.

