#### 8.9 Handling of Dropouts, Intercurrent Events, and Missing Data

In case of incomplete dates, the following approach will be used:

- If only the day is missing and the month and year are different from the month and year of the index date, the day will be imputed with 1. In case the month and year are the same as the index day the missing day will be imputed with the last day of the month.
- In case of missing months, they will be imputed
  - with July if the year is not the same as the year of the index date
  - with the following month as the month of the index date if the year is the same as the year of the index date.

If not indicated otherwise in case of completely missing dates no imputation will be done.

The MMRM analysis of the primary endpoint assumes that data are missing at random (MAR). The analysis will be conducted in ITT set and subjects will be analyzed as randomized. ITT subjects discontinue from the study for any reason without completing the study are considered intercurrent events. To assess the robustness of this MAR assumption, a conservative control-based multiple imputation method based on missing not at random (MNAR) assumption will be applied to impute missing data arising from intercurrent events for the primary endpoint analysis. In this MNAR approach, subjects who do not complete the study, missing data will be imputed by observed data obtained from the placebo group using multiple imputation with Markov Chain Monte Carlo (MCMC) simulation

method for each treatment separately. The variables for the imputation model will include MDS-UPDRS Part II score at baseline, Month 1, Month 2, Month 3, and Month 6. Approximately 50 datasets will be imputed and the same MMRM analysis as the one applied to the primary analysis will be fitted. The ROUND, MINIMUM and MAXIMUM options will be utilized to ensure imputed values are clinically plausible integers (0 – 52). The results from these 50 analyses will be combined using Rubin's rule to construct the treatment estimates from the parameter estimates and associated standard errors. The difference of the treatment means (active minus placebo) will be presented with the associated standard error and two-sided 95% confidence interval. A random seed number will be selected for the multiple imputation procedure and will be retained.

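### SAP 8.3.11.3 misfiles some partially dated medications, contradicts its own example table on missing end dates, and is not reconciled with the general date rule in SAP 8.9

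*SAP*

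**What the plan says.** SAP 8.3.11.3 sorts medications by their dates relative to study drug exposure. The definition of Prior is: "Prior medications are those for which end dates of the medication/therapy are strictly before date of first administration of study drug". Concomitant drugs are split in two: those begun strictly before first exposure (CM before in the example table) and "Concomitant medications starting on the date of first administration of study drug or after" (CM after).

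For incomplete medication dates the section adds three rules:

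- Year only: "If the only the year is available, month 6 will be imputed for the purpose of classification".
- Year and month only: "this information will be used in analogy with how complete dates are used for classification", followed by a worked table with first dose on 2020-08-14 and last dose on 2020-09-13.
- No end date: "If end date is completely missing and ongoing is not ticked, it will be assumed that the medication ended before date of first administration".

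SAP 8.9 has its own approach to incomplete dates and names no data type. If the month is missing, the date is completed "with the following month as the month of the index date if the year is the same", or with July if the year differs. If only the day is missing and the month is that of the index date, "the missing day will be imputed with the last day of the month"; in any other month, day 1 is used. The one clause in 8.9 that yields to other sections covers completely missing dates only. The term 'index date' is not defined.

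SAP 7 lists among the deviations that can exclude a subject from the per-protocol set: "Use of certain concomitant medications (for details see section 8.3.11".

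**The concern.** The Prior and Concomitant categories are meant to show which drugs were in use during treatment and which were started after it began. A rule that fills in a missing part of a date should not assert something the record cannot support. Three features of 8.3.11.3 do so or contradict one another, and 8.9 offers a programmer a second rule for the same fields.

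At stake are the Prior/Concomitant summary table and the lists by timing period. The per-protocol review could also be affected if it works from the derived category and not from the recorded dates. In a trial that allows background anti-parkinsonian therapy at stable doses, a drug started after randomization but shown as existing therapy is the kind of record a reader would want to see correctly labelled.

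**Working it through.** No sample size, power or alpha figure is involved. The check applies the written rules to the SAP's own example table and to year-only dates.

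**1. The example table under 8.3.11.3.** The table has nine rows, or 11 record types once the two rows marked No or Yes for ongoing are split. Comparing year and month directly reproduces all 11 printed categories. Applying the missing-end bullet literally reproduces 9 of 11. The entries on which the rules differ are:

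| Start | End | Ongoing | Printed | Missing-end bullet, literal | 8.9 if index date = first dose |
|---|---|---|---|---|---|
| 2020-08 | 2020-08 | – | CM before | CM before | CM after |
| 2020-08 | none | Yes | CM before | CM before | CM after |
| 2020-08 | 2020-09 | – | CM before | CM before | CM after |
| 2020-08 | none | No | CM before | Prior | not settled by 8.9 |
| 2020-09 | none | No | CM after | Prior | not settled by 8.9 |

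In the last row the bullet would end the drug before 14 August although it started in September.

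**2. Start known only to the month of first dose.** CM before requires a start earlier than first exposure. With first dose on 14 August, the start days on or after it are 14 to 31 August: 31 − 14 + 1 = 18 of 31 days (58%). The printed label is therefore not supported by the record.

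**3. Year-only end date in the year of first dose.** June lies before any first-dose month from July to December, so the record becomes Prior. Assume that the true end date is uniform over the year and the first dose falls mid-month in month m. The chance that the drug was still in use at first dose is then 1 − (m − 0.5)/12:

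- m = 7 to 12: 0.46, 0.38, 0.29, 0.21, 0.12, 0.04; sum 1.5, mean 1.5/6 = 0.25.
- Over all 12 first-dose months weighted equally: 1.5/12 = 0.125.

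For m = 1 to 6 the June end makes the record Concomitant. The chance that the drug had in fact stopped before first dose is (m − 0.5)/12, from 0.04 to 0.46, which is the mirror-image error.

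**4. SAP 8.9 applied to the same records.** This depends on the meaning of 'index date', so three readings were tried on the example table:

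- First dose: a 2020-08 start becomes 2020-08-31, and 3 of 11 record types move from CM before to CM after. All three remain Concomitant.
- First dose minus 42 days (the screening window): two record types with a 2020-08 end (starts 2020-07 and 2020-08) move from CM before to Prior.
- Last dose: the same two become Prior, and two September starts move to after treatment.

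For year-only dates in the first-dose year, with index date = first dose:

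- An end date is Prior under 8.3.11.3 and Concomitant under 8.9 for first doses in July to December (6 of 12 months).
- A start date on an ongoing drug is CM before under 8.3.11.3 and CM after under 8.9 for June to December (7 of 12).
- The two sections agree for January to May.

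A December index date would also push the following month into January, outside the recorded year.

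**5. Comparison with adverse events.** SAP 8.3.2 counts an adverse event as treatment-emergent when incomplete dates prevent a clear assignment, and SAP 8.3.12 does so for an onset in the month of first dose. An event and the drug given for it, both dated 2020-08, would be reported as a treatment-emergent event and a medication begun before treatment.

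**The case against.** The best defence is that a specific rule overrides a general one. Section 8.3.11.3 is devoted to medication dates and has a worked table. Section 8.9 never mentions medications, and adverse events have their own date rules too. On that reading, which is the natural one, the two sections do not collide. This largely stands. A reader might infer that the SAP assigns the same record to opposite categories, but the documents do not establish that: the SAP leaves precedence unstated, and which records change depends on an undefined index date. What remains is a missing sentence on precedence and a missing definition. The defects inside 8.3.11.3 do not depend on 8.9 at all.

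A second objection is that mid-year imputation is a recognised convention and that its error runs both ways. That is correct. The 25% figure describes July to December first doses only, so it cannot support a claim that the June rule generally conceals on-treatment use. In addition, SAP 8.10.2 reports enrollment complete by 9 June 2023. If enrollment means randomization, the July to December problem concerns only first doses in an earlier calendar year.

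A third is that CM before and CM after are both Concomitant, so the starts in the month of first dose discussed here do not alter the Prior/Concomitant table. This also stands; those records affect the timing split only.

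A reader might finally infer that the per-protocol set will change. The documents do not show this. SAP 7 and 8.2 leave membership to a review before unblinding that looks at protocol deviations, and SAP 8.3.4 says that eCRF data will generally be listed, so the recorded dates remain visible.

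**Conclusion.** The point holds as a defect of limited reach. SAP 8.3.11.3 as written labels some medications as Prior, or as begun before treatment, when the recorded date does not establish it, and its missing-end bullet disagrees with 2 of the 11 record types in its own table. Section 8.9 adds an unreconciled second rule.

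The consequences are confined to the Prior/Concomitant table and the timing lists, and possibly to what is seen at the blinded per-protocol review. The primary analysis is in the ITT set and uses no medication dates, so the estimate, power and type I error are unaffected. The documents do not give the number of partial medication dates. It is probably small, since medications are reviewed at every visit, and the overall effect cannot be computed. The percentages for year-only end dates rest on assumed uniform end dates and mid-month first doses. The comparisons with 8.9 rest on the stated choice of index date.

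**What to change.** Amend the SAP before unblinding:

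1. State that 8.3.11.3 governs medication dates and that 8.9 does not apply to them. Define 'index date' in 8.9.
2. Replace the month-6 imputation with one rule that matches the adverse-event convention. A medication is Prior only if the latest end date compatible with the recorded parts falls before first dose; otherwise it is Concomitant. It is 'started before' only if the latest compatible start date falls before first dose; otherwise it is 'on/after or uncertain'.
3. Say explicitly how a completely missing end date with ongoing not ticked is handled, including when the start is in or after the month of first dose. Say also whether the existing assumption for a completely missing start date stays.
4. Correct the example table to match: all rows with a 2020-08 start, and every No entry without an end date, including the 2020-07 row if the missing-end rule changes.

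The cost is a few lines of text and programming. The downside is that a few truly prior drugs will be listed as concomitant, which is the more cautious error and the one the SAP already accepts for adverse events.

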#### 8.3.12 Adverse Events

Adverse events include but are not limited to:

- worsening or change in nature, severity, or frequency of conditions or symptoms present at the start of the study;
- Subject deterioration due to primary illness;
- intercurrent illness;
- drug interaction.

An abnormal laboratory value will only be reported as an AE if the investigator considers it clinically significant, or if it leads to the Subject being withdrawn from the study.

Symptoms and conditions present at the beginning of the study will be characterized, so that AEs can be defined as any new symptom, or any increase in frequency or severity of an existing symptom.

AEs will be coded according to the most recent version of the MedDRA system and will be tabulated by system organ class (SOC) and PT.

A TEAE is an undesirable event that is not present prior to medical treatment, or an already present event that worsens either in intensity or frequency following the treatment. Only TEAEs will be included in summary tables and non-TEAEs will be listed separately.

Relationship to clinical study treatment will be mapped according to the scheme below:

- Potentially related: will include all adverse events with a relationship rating of "definitely", "probably" or "possibly".
- Unlikely/not related: will include all adverse events with a relationship rating of "unlikely" or "unrelated".

An overall summary table will give

- number of events
- number of unique events
- number of subjects with at least one event

for:

- Overall summary of TEAEs
- Serious TEAEs
- Serious TEAE related to study drug
- TEAEs related to study drug
- TEAEs by severity according to Rheumatology Common Toxicity Criteria (RCTC) categories
- TEAEs leading to treatment discontinuation of study drug
- TEAEs leading to withdrawal from study
- TEAEs leading to death

The overall summary presentation will be repeated for:

- Severity categories
- TEAEs related to study drug

The total number and percentage of subjects with at least one TEAE and the total number of TEAEs will be presented by SOC and PT.

Frequent TEAEs are defined as any PT with ≥5% incidence in any of the treatment arms, which will be summarized by PT.

Deaths, other serious AEs (SAEs), and other significant AEs will be listed, these include the following TEAEs:

- SAEs leading to death
- SAEs not leading to death
- AEs for which action was taken with study drug
- AEs leading to withdrawal from study

This listing will be divided into sub-listings with criteria as a subheading. An AE can appear in more than one sub-listing.

AE listings will include the relative time/day in relation to date and time of first administration of study drug and duration of AEs. If AE start time and time of first study drug administration is available, relative time and duration will be given as HH:MM for AEs with onset/duration less than 24 hours after first administration of study drug and otherwise as days. For AEs with incomplete dates no relative day or duration will be calculated.

If AE start date is incomplete, AEs with start month same as month of first administration of study drug will be regarded as TEAEs.

Adverse events will be reported to Data Safety Monitoring Board (DSMB) (see Section 8.11) per DSMB Charter.

#### 8.4 Other Safety Assessment

#### Vital Signs

Descriptive summaries (mean, SD, median, minimum, and maximum) of actual values and changes from baseline for all visits at which they were assessed will be calculated for systolic blood pressure, diastolic blood pressure, pulse, respiratory rate, and oral temperature.

Shift tables showing the number of subjects who shifted from normal, abnormal not clinically significant or abnormal clinically significant at baseline to normal, abnormal not clinically significant or abnormal clinically significant at each post-baseline time of assessment will be presented.

#### **Clinical Laboratory Measurements**

For continuous laboratory parameters, descriptive statistics will be presented for each visit and for the changes from baseline to each subsequent visit by treatment group.

CLINICAL SAFETY LAB TESTS					
METABOLIC PANEL	COMPLETE BLOOD COUNT	URINALYSIS			
Sodium (Na)	White Blood Cell Count (absolute and	Color			
Potassium (K)	percentage): basophils, eosinophils,	Appearance			
Chloride (Cl)	lymphocytes, monocytes, neutrophils	Specific Gravity			
Carbon Dioxide (CO2)	Red Blood Cell Count (RBC)	pН			
Blood Urea Nitrogen (BUN)	Hemoglobin (Hb)	Blood			
Glucose	Hematocrit (HCT)	Glucose			
Calcium (Ca)	Mean Corpuscular Volume (MCV)	Protein			
Creatinine (Crn)	Mean Corpuscular Hemoglobin (MCH)	Ketones			
Bilirubin (direct and Total)	Mean Corpuscular Hemoglobin	Leukocyte			
Albumin	Concentration (MCHC)	Esterase			
Protein - Total	Red Blood Cell Distribution Width (RDW)	Nitrite			
Glutamic-Oxaloacetic	Mean Platelet Volume (MPV)	Urobilinogen			
Transferase (AST, SGOT)	Platelet Count (PLT)	Bilirubin (total)			
Glutamic-PyruvateTransferase (ALT,					
SGPT)	Screening Only				
Alkaline Phosphatase (ALP)	Hemoglobin A1C (HbA1c)				
eGFR (estimated Glomerular					
Filtration Rate)					

Additionally, clinical laboratory parameters will be categorized as low, normal, or high according to laboratory range specifications and the number and percentage of subjects in each category will be presented in shift tables.

Shift tables showing the number of subjects who shifted from normal, abnormal not clinically significant or abnormal clinically significant at baseline to normal, abnormal not clinically significant or abnormal clinically significant at each post-baseline time of assessment will be presented.

Laboratory values that are outside the normal range will also be flagged in the data listings, along with corresponding normal ranges.

If laboratory values are below the limit of quantification, the value corresponding to the limit of quantification will be used when summarizing data (e.g. if the result is <x.x, then the value x.x will be used in the statistical analysis).

#### Physical Examination

Number and percentage of normal, abnormal but not clinically significant or abnormal and clinically significant findings will be tabulated by visit for the body systems:

- skin,
- head,
- eyes,
- ears,
- nose,
- throat,
- pulmonary,
- cardiovascular,

- abdomen,
- musculoskeletal,
- extremities.

Shift tables showing the number of subjects who shifted from normal, abnormal not clinically significant or abnormal clinically significant at baseline to normal, abnormal not clinically significant or abnormal clinically significant at each post-baseline time of assessment will be presented.

Physical examination data will also be presented in listings.

#### Neurological Examination

Number and percentage of normal, abnormal but not clinically significant or abnormal and clinically significant findings will be tabulated by visit for the body systems

- cranial nerves,
- strength,
- coordination,
- reflexes,
- sensation,
- tremor,
- gait,
- mental status.

Shift tables showing the number of subjects who shifted from normal, abnormal not clinically significant or abnormal clinically significant at baseline to normal, abnormal not clinically significant or abnormal clinically significant at each post-baseline time of assessment will be presented.

Neurological examination data will also be presented in listings.

